The randomisation code will be broken if a participant requires treatment for a new medical condition or experiences serious adverse reactions and either of these situations make it clinically important to know what medication they are taking. A 24/7 emergency mobile contact number will be provided on a wallet-sized card given to participants during their Research Visit. The research team member on-call will be able to contact the medical supervisor and they will make the decision to unblind. In order to unblind the participant, the medic will access the list kept in a secure cabinet at the Neurosciences Building and will disclose the allocation within a maximum of one hour. If breaking the code is necessary, only the individual's code will be broken. Data from unblinded participants will not be admitted to analysis. If unblinding occurs, the researcher will record the reason and result of the unblinding, as well as the date and time of the event.

During the week of drug/placebo administration, participants will be advised not to drink alcohol and not to carry out activities requiring full alertness, such as driving, if they are aware of any impairment. During this week, a researcher will phone up the participant on day 2 and day 4 to check that there are no concerns. Additionally,

participants will receive a text message every day reminding them to take the study medication. They will have the 24-hour contact phone number of a member of the study team and be encouraged to get in contact if they have any concerns or queries during the study week, or if their medication or health status changes.

Subsequent Visits

The Research Visit (approximately 2 hours) will take place after day 7 of atorvastatin/placebo administration. This visit will involve administration of behavioural tasks measuring emotional and reward processing. It will take place at the Neurosciences Building, Warneford Hospital.

Participants will complete the following questionnaires before the behavioural tasks:

- Positive and Negative Affect Schedule (PANAS)
- Side-effects questionnaire
- State Anxiety Inventory (state-STAI)
- Visual Analogue Scales (VAS)

Also, phlebotomy will be repeated to obtain a sample of:

- high sensitivity-C Reactive Protein

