The behavioural tasks will include the Oxford Emotional Test Battery (ETB), which has previously been found to be sensitive to the effects of antidepressants, and a reward task of Probabilistic Instrumental Learning (PIL). The ETB involves the presentation of emotion-related words and pictures of faces with different expressions. The reward task involves repeatedly choosing between two options and there is the possibility of winning up to £10 depending on the choices made (see 'Expenses and Benefits' below). All stimuli will be presented on a computer screen and participants will be required to respond via button presses on a keyboard.

Participants will be asked to report their adherence to the 7-day administration of atorvastatin/placebo.

At the end of the research visit, a member of the study team will ask participants to try to guess which treatment they received, as a measure of how successful the blinding was.

Sample Handling

Blood samples (4mL = i.e. 1 teaspoon) taken during the Screening Visit and the Research Visit for investigating hs-CRP will be handled at the Neurosciences Building's laboratory. On the same day, they will be rendered acellular by centrifugation on receipt and stored at -30°C until assay. Any excess material remaining at the end of the study will be disposed of by the laboratory within 6 months according to the Human Tissue Authority guidelines. The samples will be stored in a freezer at the Neurosciences Building in an anonymised form. Access to the samples will be by the research team and the samples will be in the custody of [name] who will hold the key code linking the samples to a particular individual. The samples will be analysed for once all participants have completed the study.

Female participants will be required to give a urine sample for a pregnancy test at the Screening Visit. Urine samples will be destroyed immediately after the test result has been obtained.

Discontinuation/Withdrawal of Participants from Study

Each participant has the right to withdraw from the study at any time. In addition, the Investigator may discontinue a participant from the study at any time if the Investigator considers it necessary for any reason including:

- Pregnancy

- Ineligibility (either arising during the study or retrospectively having been overlooked at screening)
- Significant protocol deviation
- Significant non-compliance with treatment regimen or study requirements
- Withdrawal of Informed Consent

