- Loss to follow up

If a participant is withdrawn, no further procedures or observations will continue to be required. Withdrawal from the study will result in exclusion of the data for that participant from the analysis. Withdrawn participants will be replaced. The reason for withdrawal, if given, will be recorded in the Participant Log of the Research Master File.

Definition of End of Study

The end of the study for participant involvement is the date of the last visit of the final participant.

Expenses and Benefits

Participants will be paid £100 upon completion of their participation in the research. In addition, they may win up to £10 depending on the choices they make in the reward task (see 'Subsequent Visits' above). If they do not complete the study, they will be given a pro-rata amount to recompense the time they did spend in the study. Reasonable travel expenses for any visits will be reimbursed on production of receipts, or a mileage allowance provided as appropriate.

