A serious adverse event (SAE) occurring to a participant should be reported to CTRG and the Medical Sciences IDREC where, in the opinion of the Principal Investigator, the event was ‘related’ (resulted from administration of any of the research procedures) and ‘unexpected’ (the type of event is not listed in the protocol as an expected occurrence). Reports of related and unexpected SAEs should be submitted within 15 days of the Principal Investigator becoming aware of the event. For fatal and life-threatening SUSARs, this will be done no later than 7

calendar days after the Sponsor or delegate is first aware of the reaction. Any additional relevant information will be reported within 8 calendar days of the initial report.

c) Safety of Participants

What level of baseline screening will take place for this study?

All participants will undergo a Screening Visit to ensure only eligible participants take part. The following will be recorded at baseline screening:

- Demographic information (age [years, months], years in full-time education)
- Number of cigarettes smoked per day, units of alcohol consumed per week, caffeinated drinks consumed per day
- Current and prior use of drugs (to exclude for drug use in the three months prior to the study)
- SCID-5 interview (Structured Clinical Interview for DSM-5) to probe for current or past psychiatric illness
- Beck Depression Inventory (BDI)
- Eysenck Personality Questionnaire (EPQ)
- State and Trait Anxiety Inventory (STAI)
- Positive and Negative Affect Schedule (PANAS)
- Snaith-Hamilton Pleasure Scale (SHAPS)
- Side-effects questionnaire
- Visual Analogue scales (VAS)

To ensure it is safe to administer the drug to the participant, the following will be recorded:

- Weight, height, and BMI
- Medical history (including family psychiatric history)
- Details of current and past medication
- Urine pregnancy test (female participants only)

Also, phlebotomy will be undertaken to obtain a sample of:

- high sensitivity-C Reactive Protein

Participation in prior studies will be recorded to exclude for individuals who have used the same/similar emotional processing tasks.

Provide details about the safety monitoring of participants and the staff/researchers carrying this out

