Statins are considered extremely safe drugs: their more common side-effect are muscle pain or weakness (usually mild and quickly responding to stopping or switching medication) and elevation of liver transaminases (significant only in case of pre-existing hepatic disease), whereas more serious adverse events include rhabdomyolysis (very rare but severe myopathy associated with elevated creatine kinase and myoglobinuria), new-onset diabetes mellitus (in predisposed individual with pre-existing hyperglycaemia), and haemorrhagic stroke (in patients with prior haemorrhagic stroke or lacunar infarct); however, clinical trials have ultimately concluded that such adverse events attributed to statin therapy in routine practice are not actually caused by it (Collins-2016), especially at doses lower than 80mg/day and when used for less than 52 weeks (Li-2016). Other common ($\geq 1/100$, $< 1/10$) but usually mild side-effects include: nasopharyngitis, pharyngo-laryngeal pain, epistaxis, headache, and gastrointestinal disturbances (constipation, diarrhoea, flatulence, dyspepsia, nausea). The potential side-effects and adverse events will be clearly stated in the Participant Information Sheet and researchers will discuss these with participants as part of the informed consent procedure.

To minimise the risk associated with side-effects, participants will be contacted on days 2 and 4 of the study week by a named researcher to check there are no concerns. All participants will have 24-hour contact details of a named researcher who they can contact during the study period. The named researcher will in turn contact a qualified medical doctor if necessary. In order to limit the risks associated with fatigue, during the week of statin/placebo administration, participants will be advised not to drink alcohol, and not to carry out activities requiring full alertness if they are aware of any impairment.

If judged necessary by the medical lead, the randomisation code will be broken for that individual by the medical supervisor and the participant will be advised to stop taking the medication and withdrawn from the study.

Will the research involve deliberate deception of participants?
 
If yes, justify why deception is used, describe deception and debriefing process, and include debriefing documents in the application
	Yes 	No 
---	------------------------------	--

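### A participant whose code is broken for a reaction is withdrawn, with no required follow-up to resolution and no place in the side-effects comparison

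*Combined protocol and SAP*

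**What the plan says.** Two places describe when the code is broken. Section 6 (Study Procedures) sets a high threshold: a serious adverse reaction, or a new condition needing treatment, where knowing the allocation matters clinically. Section 8(d) (Ethical Considerations), directly after the account of side-effect risks, leaves it to the medical lead's judgement and adds that "the participant will be advised to stop taking the medication and withdrawn from the study".

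The consequences are in section 6:

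- On unblinding: "Data from unblinded participants will not be admitted to analysis". The event is documented: "the researcher will record the reason and result of the unblinding, as well as the date and time of the event".
- On withdrawal: "If a participant is withdrawn, no further procedures or observations will continue to be required". Also: "Withdrawal from the study will result in exclusion of the data for that participant from the analysis". The participant is replaced, and the reason for withdrawal, if given, goes in the participant log.

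Section 9 (Statistics and Analysis) repeats the exclusion of withdrawn participants. It lists side-effects among the measures to be analysed by repeated measures ANOVA and makes no exception for safety data.

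The safety provisions are calls on days 2 and 4 of the dosing week, a doctor who is contacted if a participant raises side-effects or a change in health during that week, and a contact number: "All participants will have 24-hour contact details of a named researcher who they can contact during the study period". Section 8(b) adds reporting of serious adverse events that are related and unexpected.

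**The concern.** Stopping the capsules and leaving the study are separate decisions, and section 8(d) makes them one step. The participants on this route are healthy volunteers with no expected benefit whose reaction, or new condition, was serious enough to break the blind. They are the people for whom a plan would normally require more observation, and here the requirement ends.

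Two things are at stake. The first is participant safety. The protocol reassures the reader that muscle symptoms settle soon after the drug is stopped, but it asks nobody to confirm this. GPs are not told of participation (section 8(c)), so the plan alerts no outside clinician. The second is the side-effects result. The most severe reactions are left out by rule and the places are filled by other people, so a reader of the final comparison would see full arms and no sign of the omission.

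**Working it through.** The plan gives no figure on this point, so the check is to follow one participant through the rules.

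**Step 1: code break.** A participant has a serious reaction on, say, day 4. A doctor decides to unblind (section 6). Under section 8(d) the participant is told to stop and is withdrawn. Section 6 also has a discretionary route, under which "the Investigator may discontinue a participant from the study at any time". Anyone withdrawn that way meets the same rules from step 2 on.

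**Step 2: follow-up.** After withdrawal no observation is required. The provisions that remain compare as follows:

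| Provision | Section | Follow-up to resolution? |
|---|---|---|
| Calls on days 2 and 4 | 6, 8(c), 8(d) | No: tied to the dosing week and not required after withdrawal |
| 24-hour contact number | 6, 8(c), 8(d) | No: the participant must call |
| Doctor contacted about side-effects | 8(c) | No: prompted by a concern the participant raises in the study week |
| Unblinding record and participant log | 6 | No: they record the event, not how it ended |
| Serious adverse event reporting | 8(b) | No: a report to oversight bodies, limited in scope |

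On the last row, an event counts as unexpected when "the type of event is not listed in the protocol as an expected occurrence". Muscle pain and rhabdomyolysis are both named in the synopsis and in section 8(d). Even a serious case can therefore be read as expected and outside the reporting rule. The provision for additional information within 8 days applies only once an initial report has been made.

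**Step 3: data.** The side-effects questionnaire is given at screening and at the Research Visit after day 7, and at no other time. There are two cases:

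- Withdrawn before the Research Visit: no post-baseline score is required, so there is probably none.
- Unblinded at or after the Research Visit: a score may exist, but the exclusion rules remove it.

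Two separate rules exclude the participant, one for unblinding (section 6) and one for withdrawal (sections 6 and 9). Relaxing only one would change nothing. In the first case, relaxing both would still recover no score, because none was collected.

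**Step 4: the comparison.** After replacement, the side-effects ANOVA has its planned 25 per group if replacements take the same allocation, which the plan does not state. It contains only people who finished. If stops fall mainly on atorvastatin, the difference between arms will look smaller than it was. If they fall evenly, no direction can be given.

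**The case against.** The strongest case on the other side has four parts.

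- **The route is narrow and a doctor is already on it.** The section 6 threshold is high, and the medical lead or supervisor has judged the case before the code is broken. The withdrawal wording reads naturally as ending research obligations, not care. This stands. A reader might infer that the plan forbids follow-up or abandons the participant. The text does not say so: it only fails to require follow-up. Nor would ordinary muscle pain, which the protocol calls usually mild, normally meet the threshold.
- **Comparing adverse reactions is not an aim.** The synopsis says the study is not designed for that, and side-effects are neither a primary nor a secondary outcome. This limits the weight of the point. But section 9 does plan a side-effects analysis, and its result should state whom it describes.
- **No size can be given.** A reader might take the frequency band in section 8(d), 1/100 to under 1/10, and compute 25 x 0.01 = 0.25 to 25 x 0.10 = 2.5 drug-arm cases per listed effect. The documents do not support using this as a code-break rate. The band belongs to a separate list of usually mild effects such as headache and nasopharyngitis, and the share leading to a code break is unknown and may be zero. A shift in the drug-arm mean would also need the number of stops, how much worse those participants would have scored, and the arms of both the stops and the replacements. None of these is given.
- **The Participant Information Sheet may say more.** It was not available for this review. It could inform participants about follow-up, but it would not alter the exclusion rules as written.

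**Conclusion.** The point holds as a matter of written procedure. A code break for a reaction leads to withdrawal. Withdrawal ends required observation. The participant's data, safety data included, are then excluded and the place refilled. The plan therefore requires no follow-up of the reaction to resolution, and its side-effects comparison is a completer comparison without saying so.

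The route is probably rare: dosing lasts seven days, in screened healthy volunteers, with a licensed drug. No numerical bias is claimed, and with no such stops the analysis is unaffected. The stated power and the primary and secondary outcomes are not affected by this point. The safety part needs no rate, because a single case is enough for it to matter. The conclusion rests on the protocol text and assumes that no document outside it, such as the information sheet, already requires follow-up. The change should be made because it is cheap and specific. The point is not a reason to doubt the main design.

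**What to change.** **Sections 6 (withdrawal) and 8(d).** State that a participant stopped for an adverse reaction is contacted by the study doctor until it resolves, unless consent for contact is withdrawn. State also that the participant completes the side-effects questionnaire at stopping, by phone if needed, and that a score taken after unblinding is marked as such. Say explicitly that the withdrawal rule does not end this follow-up. Which reactions lead to stopping remains a clinical decision.

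**Sections 6 (unblinding and withdrawal) and 9.** Exempt safety data from both exclusion rules. Report stops for adverse reactions, with their outcomes, by arm for everyone who took a capsule. Label the side-effects ANOVA as a completer analysis and show the new table beside it. Stop-day scores should not be pooled into the ANOVA, since they are taken on a different day. The ANOVA itself therefore does not change; the table makes visible what it omits.

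**Cost.** One questionnaire and a few calls per stopped participant, one extra table and a few sentences of protocol text, with no new visits. The downside is that some stop-day scores will be unblinded and not comparable with day-7 scores.

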9. STATISTICS AND ANALYSIS

Do you have a statistical plan?

Yes No

If no, please justify.

The IBM SPSS statistical software will be used to analyse all behavioural data. Demographic and baseline measures will be analysed using independent t-tests.

Mood, anxiety, side-effects, and hs-CRP measures will be analysed using repeated measures analysis of variance (ANOVA).

Behavioural task results will be analysed using between-groups analysis of variance (ANOVA).

Any significant interactions will be followed up using simple main effect analyses. When assumptions of equality of variances are not fulfilled, the Greenhouse-Geisser procedure will be used to correct the degrees of freedom.

Number of Participants

50 healthy volunteers (25 per group)

Have you done a sample size calculation?

Yes No

If yes, please give details below

If no, please give details to indicate you have considered the implications the selected sample size will have on the study outcome

We will be using the Oxford Emotional Test Battery, which is a well-validated set of emotional processing tasks that are sensitive to antidepressant effects. On the facial expression recognition task, one of the main outcome variables is accuracy at recognising fearful facial expressions and a sample size of 25 per group would give 0.9 power to detect changes of the magnitude of those we have seen in a previous antidepressant healthy volunteer study [drug mean 10.64 (SD 9.77) vs placebo mean 3.36 (SD 5.96) (Harmer-2004).

Analysis of Outcome Measures

Data analysis will take place at the University of Oxford, Department of Psychiatry, and will be undertaken by the research team under the supervision of the Principal Investigator. All data will be analysed using a between-groups analysis of variance (ANOVA).

Withdrawn participants' data will not be included in the analysis.

The primary outcome measure is performance (accuracy and reaction time) in computer-based tasks of emotional processing in the comparison between drug and placebo groups. Secondary to this is performance (accuracy and reaction time) in a computer-based task of reward processing in the comparison between drug and placebo groups, and changes in high sensitivity-C Reactive Protein (hs-CRP) from baseline to seven-day in the comparison between drug and placebo groups.

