2. SYNOPSIS

Please state why this study is not considered a Clinical Trial of an Investigative Medicinal Product
	
This study is not a Clinical Trial of an Investigative Medicinal Product as we are not investigating the efficacy of atorvastatin but using it as a pharmacological tool to understand the role of inflammation in emotional and reward processing.
 
This study does not fit the MHRA definition of a clinical trial as one designed to: discover or verify/compare a drug's clinical effects; to discover or verify/compare its pharmacological effects (e.g. pharmacodynamics); to identify or verify/compare its adverse reactions; or to study its absorption, distribution, metabolism or excretion (https://www.gov.uk/government/uploads/system/uploads/attachment_data/file/317952/Algothrim.pdf).
	

List all sites where study will be conducted
	
Neurosciences Building, Department of Psychiatry, University of Oxford, Warneford Hospital, [name]
	

Age Range of Study Participants
	
18-50 years old
	

Planned Sample Size
	
50 healthy volunteers (25 per group)
	

Planned Study Duration (n.b. A minimum approval period of 1 year and maximum of 5 years can be granted)
	
24 months
	

Anticipated Start Date
	
1st February 2019
	

Anticipated End Date
	
1st February 2021
	
	
Objectives
	
Outcome Measures

Primary
	
To investigate the effects of seven-day atorvastatin administration on emotional processing
	
Accuracy and reaction times on computer-based tasks of emotional processing (e.g. facial expression recognition, emotional categorisation and memory), comparing those receiving drug and placebo.

Secondary
	
To investigate the effects of seven-day atorvastatin administration on reward processing
	
Accuracy and reaction times on computer-based tasks of reward processing comparing those receiving drug and placebo.

	To investigate the effects of seven-day atorvastatin administration on inflammation	Changes in high sensitivity-C Reactive Protein (hs-CRP) from baseline to seven-day, comparing those receiving drug and placebo
Name of drug/substance	Atorvastatin	

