6. STUDY PROCEDURES

Baseline Assessments and Procedures

Individuals who are interested in participating in the study will be invited to attend a Screening Visit (maximum 2 hours) at the Neurosciences Building, Warneford Hospital.

Demographic information will be collected:

- Age (years, months), years in full-time education

Participants' eligibility to take part will be checked by recording the following:

- Weight, height, and BMI
- Medical history (including family psychiatric history), details of current and past medication
- Current and prior use of drugs (to exclude for drug use in the three months prior to the study)
- Menstrual cycle (in order to avoid scheduling testing in the premenstrual week)
- SCID-5 interview (Structured Clinical Interview for DSM-5) to probe for current or past psychiatric illness
- Urine pregnancy test (female participants only)

The following baseline assessments will be completed (APPENDIX F: QUESTIONNAIRES):

- Beck Depression Inventory (BDI)
- Eysenck Personality Questionnaire (EPQ)

- Positive and Negative Affect Schedule (PANAS)
- Side-effects questionnaire (to determine baseline of bodily symptoms/'side-effects')
- Snaith-Hamilton Pleasure Scale (SHAPS)
- State and Trait Anxiety Inventory (STAI)
- Visual Analogue Scales (VAS) measuring subjective state

Also, phlebotomy will be undertaken to obtain a sample of:

- high sensitivity-C Reactive Protein

Participants will be asked to wait while their eligibility to take part is assessed by a medical doctor involved in the study (maximum 30 minutes). Any participant for whom additional information is required before an eligibility judgment can be made will be asked to return on a different day once this information has been obtained.

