Eligible participants will be randomised to receive either 7-day atorvastatin 20mg (25 participants), or 7-day placebo (25 participants) administration. Randomisation will occur on the day of screening, or up to a maximum of 4 weeks after screening. Randomisation after the Screening Visit will occur in the event that further information is needed before determining whether participants are eligible to take part (for example, if a participant needs to follow-up with details of allergies, or previous studies they have taken part in). In this case, if more than 4 weeks have elapsed, another Screening Visit will be performed to ensure participants are still eligible. The randomisation code will be drawn up by a researcher not involved in the study using an online randomisation tool (<https://www.sealedenvelope.com/simple-randomiser/v1/lists>). Randomised participants will be given 7 days of the drug to take home, as well as full instructions of how and when to take them.

The atorvastatin drug and the placebo will be provided by the Oxford Pharmacy Stores and will be encapsulated at the Neurosciences Building according to previously agreed standard operating procedures (APPENDIX G: Neurosciences, SOP Number: Encapsulation Version 2: 22.10.2012). Blinding will be achieved by the identical matching of the atorvastatin and placebo treatments. Participants will not be aware of the treatment that they will be receiving; neither will the researcher, as this study is double-blind.

Allocation of treatments will be recorded on a Randomisation List, which will be updated when each new participant enters the randomised phase. The list will be held at the Neurosciences Building by a scientist uninvolved in the study.

The study medication and placebo will be stored in a secure environment at the Neurosciences Building accessible only to staff. It will be stored at room temperature and accounted for using agreed study documentation. Using the Randomisation List and the participant's unique randomisation code, staff will determine whether to dispense active or placebo tablets.

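### Measures taken at both visits (hs-CRP, PANAS, state anxiety, VAS, side-effects) have two named analyses, and neither uses the screening value as a covariate

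*Combined protocol and SAP*

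**What the plan says.** Section 9 (Statistics and Analysis) names two analyses for the same measures. The statistical plan says "Mood, anxiety, side-effects, and hs-CRP measures will be analysed using repeated measures analysis of variance (ANOVA" and gives the behavioural tasks a between-groups ANOVA in a separate sentence. Further down, under Analysis of Outcome Measures, it says "All data will be analysed using a between-groups analysis of variance (ANOVA". The only other stated use of baseline data is "Demographic and baseline measures will be analysed using independent t-tests".

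The Synopsis defines the hs-CRP outcome as "Changes in high sensitivity-C Reactive Protein (hs-CRP) from baseline to seven-day, comparing those receiving drug and placebo", and Section 9 repeats the change wording. No change outcome is stated for mood, anxiety or side-effects.

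Section 6 (Study Procedures) shows that the baseline values exist. At screening, "The following baseline assessments will be completed (APPENDIX F: QUESTIONNAIRES" introduces a list that includes PANAS, the side-effects questionnaire, the STAI and VAS, and blood is taken for hs-CRP. At the Research Visit, "Participants will complete the following questionnaires before the behavioural tasks" introduces PANAS, side-effects, state anxiety and VAS, and "Also, phlebotomy will be repeated to obtain a sample of" covers hs-CRP. No transformation is given for hs-CRP.

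**The concern.** There are three linked problems.

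- **Precision.** Repeated-measures ANOVA uses the screening value by subtraction, and a between-groups ANOVA of the day-7 value does not use it at all. The change score is inefficient when r is low and the day-7 comparison is inefficient when r is high. ANCOVA estimates the weight from the data, so nobody has to guess r.
- **An open choice of test.** A between-groups ANOVA agrees with the group-by-time test only if it is run on change scores. The hs-CRP outcome is worded as a change; the others are not. Nor does the plan say which term of the repeated-measures ANOVA is the treatment test.
- **Scale.** If hs-CRP is right-skewed, the choice between raw and log values changes power considerably, and the plan leaves that choice open.

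The study uses the drug as a tool to examine the role of inflammation, and hs-CRP is the only measure of it. The precision of that comparison decides how far a null result can be read.

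**Working it through.** **The plan's own power figure.** Section 9 gives 0.9 power with 25 per group for means 10.64 (SD 9.77) and 3.36 (SD 5.96). The difference is 7.28, the pooled SD √((9.77² + 5.96²)/2) = 8.09, and d = 0.90. Two-sided at 0.05, the normal approximation gives 0.889 and the t-test 0.876. This concerns a task measured once and does not depend on what follows. No power is stated for the measures taken twice.

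**Inputs.** From the documents: 25 per group. Assumed, because not stated: alpha 0.05 two-sided, r over a range, roughly normal data and equal variances at both visits.

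**Identity.** With two time points, the group-by-time F equals the squared t on change scores. On one simulated dataset both were 10.888, while the squared t on day-7 values was 9.719.

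**Variance of the treatment difference, relative to day-7 only (= 1).**
- Change score: 2(1 − r).
- ANCOVA: (1 − r²) × 47/46, where 47/46 is the cost of chance baseline imbalance with 50 participants. At r = 0.5 this is 0.75 × 1.0217 = 0.766.

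Power is from the noncentral t with 48 df (47 for ANCOVA), with noncentrality δ/√(2 × factor/25). At r = 0.5 and δ = 0.8 SD this is 0.8/√(2 × 1.000/25) = 2.83 for change and 0.8/√(2 × 0.766/25) = 3.23 for ANCOVA.

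| r | Variance: change | Variance: ANCOVA | ANCOVA vs change | ANCOVA vs day-7 | Power at 0.8 SD: change / day-7 / ANCOVA |
|---|---|---|---|---|---|
| 0 | 2.000 | 1.022 | −49% | +2% | 0.50 / 0.79 / 0.78 |
| 0.3 | 1.400 | 0.930 | −34% | −7% | 0.65 / 0.79 / 0.82 |
| 0.5 | 1.000 | 0.766 | −23% | −23% | 0.79 / 0.79 / 0.89 |
| 0.7 | 0.600 | 0.521 | −13% | −48% | 0.95 / 0.79 / 0.97 |
| 0.9 | 0.200 | 0.194 | −3% | −81% | 1.00 / 0.79 / 1.00 |

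At an assumed 0.5 SD effect, power (same order) is 0.41 / 0.41 / 0.51 at r = 0.5 and 0.61 / 0.41 / 0.67 at r = 0.7.

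**Break-even.** Against day-7: (1 − r²) × 47/46 = 1 gives r = √(1/47) = 0.146. Against change: (1 + r)/2 × 47/46 = 1 gives r = 45/47 = 0.957.

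**Unspecified term.** If the group main effect were read as the treatment test, it would average in the pre-treatment value. Its variance factor is 2(1 + r), or 3.0 at r = 0.5, and power for 0.8 SD is about 0.36.

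**Two tests available.** In 20,000 simulated null trials, at least one of the change and day-7 tests reached p < 0.05 in 8.8%, 9.0% and 9.3% at r = 0.3, 0.5 and 0.7.

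**hs-CRP scale.** This assumes log-normal values, r = 0.5 and hs-CRP halved on drug (20,000 trials per cell).

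| Log-SD | Raw change | Raw ANCOVA | Log change | Log ANCOVA |
|---|---|---|---|---|
| 0.8 | 0.51 | 0.81 | 0.85 | 0.93 |
| 1.0 | 0.31 | 0.56 | 0.67 | 0.78 |
| 1.2 | 0.20 | 0.36 | 0.52 | 0.63 |

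For a 20% fall, log ANCOVA reaches only about 0.20, 0.15 and 0.12, so every option would usually miss it.

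**The case against.** The planned group-by-time test is valid, and leaving out ANCOVA is a loss of efficiency, not an error. That stands. The gain over change also shrinks as r rises: 8% of variance at r = 0.8 and 3% at 0.9.

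The conflict may be loose wording. The specific assignment of repeated-measures ANOVA could be taken to govern, and Section 9's line on following up significant interactions fits a group-by-time reading. For hs-CRP, the change wording makes the two analyses agree. This narrows the ambiguity to mood, anxiety and side-effects, which are not listed as outcomes. It does not remove the literal conflict, since the behavioural tasks already have their own between-groups sentence, and it supplies no covariate.

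The 9% figure needs both tests to be run and either one claimed, which the plan does not propose. It shows what an open choice could cost; it does not predict what will be done.

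Much of the hs-CRP gain comes from the log scale and not from the covariate, and skewness is assumed. That is also right, so scale is treated as a separate decision.

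Finally, ANCOVA on change with baseline as covariate gives the same treatment estimate as ANCOVA on the day-7 value, so ANCOVA alone would not force a new hs-CRP outcome definition. Side-effect scores in healthy volunteers may also sit near the floor, where a linear model fits less well.

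**Conclusion.** The concern holds. Five measures are taken twice, two analyses are named for them, and neither uses the screening value as a covariate. ANCOVA is more precise than both alternatives for r between about 0.15 and 0.96. At r = 0.5 the variance falls by 23% against either, and power for a 0.8 SD effect rises from 0.79 to 0.89. The size depends on r, which the documents do not give, and on the normality and equal-variance assumptions above. The log-scale figures rest further on assumed right skew.

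The scope is one secondary outcome and supporting measures in a study described as exploratory. The behavioural tasks are done only at the Research Visit, so the primary outcome and the sample-size calculation are unaffected. This is a change that should be made, because it is nearly free. It is not a flaw that invalidates the plan.

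**What to change.** 1. In Section 9, limit the all-data sentence to measures taken once, namely the behavioural tasks.
2. Replace the repeated-measures sentence with: *Research Visit hs-CRP, PANAS, state anxiety, VAS and side-effect scores will be analysed by ANCOVA with treatment and the screening value of the same measure, reporting the adjusted difference with 95% CI.*
3. Fix the hs-CRP scale before unblinding. Log is proposed if right skew is expected, with a stated rule for values below the assay limit and the result given as a ratio of geometric means.
4. Align the hs-CRP outcome wording in the Synopsis and Section 9 with the chosen analysis. This matters mainly if the log scale is adopted.

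The cost is wording only, with no new data. ANCOVA uses one error degree of freedom (48 to 47). In the worst case, r near 0, its variance is about 2% above that of the day-7 comparison, and below r of about 0.15 it gains nothing over it. The timing rule "Randomisation will occur on the day of screening, or up to a maximum of 4 weeks after screening" means baseline can precede treatment by up to four weeks, which may lower r. Low r is also where the change score performs worst. The log scale changes the reported effect to a ratio.
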